into the FEM software (Comsol Inc., Burlington, MA). The FEM is used to calculate the light propagation and absorption in the 3-D model. **Figure 3** shows the results of a simulation that was conducted on a model created from de-identified CT scans of a patient with locally advanced NSCLC. The de-identified scans were obtained with approval from the Roswell Park Cancer Institute Office of Research Subject Protection. This was a proof-of-concept simulation to assess the possibility of delivering sufficient light dose to a tumor that could be amenable for EBUS-TBN guided I-PDT. The simulations suggest that by interstitial illuminating of the tumor with seven fibers (RD250) with 4 cm cylindrical diffuser end each, we can administer a light dose of 56.5 J/cm² to 100% of the tumor. Each fiber delivers the FDA approved laser light intensity of 400 mW/cm and energy of 200 J/cm. In this large tumor, the overall I-PDT treatment time would be about 1 hr, when fiber is illuminated for 500 s each time.

Recent preclinical studies in [name] laboratory suggest that the irradiance has an important impact on tumor response, for I-PDT of locally advanced head and neck cancer. (40, 41) We believe that this is also true for I-PDT in LALC. However, in EBUS guided I-PDT for LALC, we are limited in the number and location of fibers that we can insert into the tumor. In this exploratory study we will aim to administer the new light settings to a significant volume of the target tumor. We will administer a 630-nm laser light with the objective to deliver a minimal irradiance of ≥ 8.6 , ≥ 10.8 or ≥ 15.3 mW/cm² where we reported effective ablation in Oakley et al. 2020. (41) The treatment time will be adjusted to deliver ≥ 45 J/cm² to a significant volume of the target tumor. The research team will present a table showing the light delivery options and percent of tumor volume that will receive the minimal irradiance and fluence for the physician to review.

[figure not shown]

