- o At [name] laboratory, both DOSIE[™] and COMSOL[™] will be used to generate treatment planning for 630-nm laser. Each plan will use the same number and location of the fiber placement, diffuser length, and intensity (W/cm). The software packages will be used to compute the irradiance and fluence required to administer our target irradiance of ≥ 8.6 mW/cm² in a significant volume of the target tumor. The plans will also suggest the treatment time to deliver ≥45 J/cm² to a significant volume of the target tumor.
- For each plan, the research team will generate a table showing the light delivery options and percent of tumor volume that will receive the minimal and maximal irradiance and fluence for the physician to review.
- The research team will compare the DOSIETM computation with the COMSOLTM. Although both use same input, the differences in the mesh generation and the solvers used in the simulations could impact the resulted irradiance and fluence. The comparison will include percent of tumor that receive ≥ 8.6 mW/cm² and ≥ 45 J/cm², the irradiance and fluence at the margins, the minimum, average, and maximum irradiance and fluence in 100% of the tumor. If there is disagreement (more than 5% difference) we will use COMSOLTM computation.
- The treating physician will review the plan and either approve or request changes.
 - Several iterations (typically 1-3) may be required until the treating physician approves the plan. The review will be in-person or via secured web-based communication (e.g., password protected Microsoft Teams).
 - Once approved, a detailed description of the plan will be provided via secured e-mail.
- The I-PDT procedure will follow the plan as much as possible, taking into consideration patient safety, and treatment time.
 - \circ Our previous studies suggest that fiber placement within ≤ 10 mm from the planned placement will have insignificant impact on the total light irradiance and fluence in the target tumor.

• The difference between the planned and actual placement of the fibers will be recorded (using EBUS imaging and measurements). These data will be used for post analysis, to calculate the actual light distribution by DOSIE[™] and COMSOL[™].

Extrabronchial tumors that are identified by EBUS will be treated with I-PDT. The laser fiber will be inserted into the tumor using the EBUS-TBN. The I-PDT procedure will follow these steps:

- Curvilinear Endobronchial Ultrasound will be used to identify the tumor.

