- The laser fiber will be placed within the target tumor under EBUS guidance in one to 10 locations, sequentially. The number and location of the fiber placement will be according to a pre-treatment planning (as much as possible), as the example shown in **Figure 3**.

- If possible (i.e., optional), optical measurement of light transmission and tumor pO2 will be performed before and after I-PDT as described in **section 1.1.13**
- Using either fiber, a 630-nm laser light will be administered with the objective to deliver a minimal irradiance of ≥ 8.6, ≥ 10.8 or ≥ 15.3 mW/cm² to a significant volume of the target tumor, based on Oakley et al. 2019. The treatment time will be adjusted to deliver ≥ 45 J/cm² to a significant volume of the target tumor. The research team will present a table showing the light delivery options and percent of tumor volume that will receive the minimal irradiance and fluence for the physician to review.
- The pre-treatment plan will be presented to the treating physician (the investigator) for review and approval. The investigator will decide how many insertions will be made and where the fiber(s) will be inserted, using clinical judgment and taking into account the patient's safety.
- The I-PDT procedure should be complete within a few hours.
- Airway stenting will be performed after I-PDT, as needed.
 - For cases where airway stenting is indicated to secure the airway, EBUS will be performed before or after airway stenting, as necessary, and the identified portion of the tumor will be evaluated and treated with I-PDT.

At least one tumor will be treated during the I-PDT. The treating physician will determine how many tumors will be treated, taking into account the patient's safety.

6.1.3 Endobronchial tumors that are identified with endoscopy and prior CT or MRI will be treated with I-PDT and/or PDT

- The laser fiber will be placed in the tumor for I-PDT or in the airway for PDT.
- A 630-nm laser light will be administered with the objective to deliver a minimal irradiance of ≥ 8.6, ≥ 10.8 or ≥ 15.3 mW/cm² to a significant volume of the target tumor, based on Oakley et al. 2020. (41) The treatment time will be adjusted to deliver ≥ 45 J/cm² to a significant volume of the target tumor. The research team will present a table showing the light delivery options and percent of tumor volume that will receive the minimal irradiance and fluence for the physician to review.

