12.1.4 Secondary Analysis

For both Cohort 0+A combined and Cohort B progression free survival (PFS) will be defined as the time from date of study treatment to the time of first observed disease progression (modified RECIST 1.1 criteria) at the treated tumor site or death due to any cause. PFS will be summarized using standard Kaplan-Meier methods, with median PFS and specified PFS rates estimated with 95% confidence intervals. The number of bronchoscopies will be summarized descriptively.

For Cohort A only we will measure agreement between DOSIETM and COMSOLTM treatment planning measures in n=18 subjects consisting of light intensity from each fiber (mW, and mW/cm), percent of tumor that receives ≥ 8.6 mW/cm² and ≥ 45 J/cm², the irradiance and fluence at the margins, the min, average and maximum irradiance and fluence in 100% of the tumor using the concordance correlation coefficient (76)(CCC) and Bland-Altman plots (77) for visual displays of agreement. We will calculate the one-sided 95% confidence interval for the CCC using a percentile bootstrap-t approach for each endpoint and we will calculate the 95% confidence interval display. Disagreement on a given measure will be inferred if the estimated CCC is below the lower bound of the one-sided 95% percentile confidence interval.

Tumor response as a function of STAT3 tumor conversion percentages (if possible) will be analyzed using logistic regression adjusted for age and sex.

The data from this trial will inform the design of a prospective Phase IIb randomized trial.

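### The irradiance target is one level in the planning steps and three in the delivery steps, and DOSIE-COMSOL agreement on tumor coverage is checked only at the lowest level

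*Combined protocol and SAP*

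**What the plan says.** The pre-treatment planning steps in 6.1.2 give one irradiance target. Both packages are used to find the irradiance and fluence "required to administer our target irradiance of ≥ 8.6 mW/cm² in a significant volume of the target tumor". The fluence aim follows: "The plans will also suggest the treatment time to deliver ≥45 J/cm² to a significant volume of the target tumor".

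The delivery steps later in 6.1.2 set the objective to "deliver a minimal irradiance of ≥ 8.6, ≥ 10.8 or ≥ 15.3 mW/cm² to a significant volume of the target tumor", and 6.1.3 repeats the same three levels for endobronchial tumors. The background on treatment planning, section 1.1.9, also lists three, ending "or ≥ 15.3 mW/cm² where we reported effective ablation".

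On the choice among them, 1.1.9, 6.1.2 and 6.1.3 provide a table of light delivery options with the percent of tumor volume covered. The treating physician reviews the plan and approves it or asks for changes.

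On comparing the software, 6.1.2 states: "The comparison will include percent of tumor that receive ≥ 8.6 mW/cm² and ≥ 45 J/cm²". It adds irradiance and fluence at the margins and "the minimum, average, and maximum irradiance and fluence in 100% of the tumor". If the packages differ by more than 5%, the COMSOL computation is used. Section 12.1.4 assesses agreement in the 18 Cohort A patients with the concordance correlation coefficient and Bland-Altman plots. Its coverage measure is "percent of tumor that receives ≥ 8.6 mW/cm² and ≥ 45 J/cm²", alongside per-fiber light intensity and the same margin, minimum, average and maximum measures.

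**The concern.** Light is half of the dose in this treatment, and 1.1.9 itself says that irradiance matters for tumor response. A reader of 6.1.2 cannot tell whether 8.6 mW/cm² is the target or one of three permitted targets. Nor does the text say, if there are three, what decides which one a patient's plan is built to.

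Two analyses depend on the answer. The first is the DOSIE-COMSOL comparison, a Cohort A secondary objective that also decides in practice which computation is used. If a plan is approved on its coverage at 10.8 or 15.3 mW/cm², the coverage comparison is made at a different threshold from the one that mattered. The second is the secondary objective relating irradiance and fluence to response. It needs to know what each plan aimed for as well as what the tumor received.

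**Working it through.** **1. The passages side by side.**

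| Place | Irradiance (mW/cm²) | Fluence (J/cm²) |
|---|---|---|
| 1.1.9, planning background | ≥8.6, ≥10.8 or ≥15.3 | ≥45 |
| 6.1.2, planning steps | ≥8.6 | ≥45 |
| 6.1.2, delivery steps | ≥8.6, ≥10.8 or ≥15.3 | ≥45 |
| 6.1.3, endobronchial tumors | ≥8.6, ≥10.8 or ≥15.3 | ≥45 |
| 6.1.2, software comparison | coverage at ≥8.6 | coverage at ≥45 |
| 12.1.4, Cohort A agreement | coverage at ≥8.6 | coverage at ≥45 |

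Fluence is consistent throughout. Irradiance is not.

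**2. The span of permitted targets.** Ratio = higher level / lower level.

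- 10.8 / 8.6 = 1.26
- 15.3 / 10.8 = 1.42
- 15.3 / 8.6 = 1.78

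**3. Is there a criterion?** The documents give a process: an options table, then physician review and approval. For the investigator's own decision, the delivery steps mention the number and position of fiber insertions or placements. They do not mention the irradiance level. No section says which level applies to which patient or tumor.

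**4. Could both versions be true?** The levels are nested, since a volume receiving at least 15.3 also receives at least 8.6. If 8.6 is the only binding floor, the other two levels in the delivery steps have no stated function. If all three are real options, the planning steps are incomplete. Either reading needs a text change.

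**5. Do the other measures cover the gap?** Let V(x) be the fraction of tumor volume with irradiance of at least x. The coverage measure is V(8.6). The minimum and maximum mark where the V curve leaves 1 and reaches 0, and the average irradiance is the area under it. Fixing those three and V(8.6) does not fix V(10.8) or V(15.3). Two packages can agree on all four and still differ on the volume above the higher levels. Irradiance at the margins describes the boundary, not the volume. Per-fiber intensity is no substitute either, because 6.1.2 has both plans use the same intensity. So agreement on V(10.8) and V(15.3) is neither measured directly nor implied by what is measured, and a difference in either is not among the listed inputs to the 5% rule.

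**The case against.** The strongest reply is that 8.6 can be read as a floor, that individualized dosimetry is the intervention under study, and that the physician approves each plan from a table of options over what 6.1.2 describes as typically one to three iterations. Much of that stands. There is a process, so what is missing is a criterion. The split is not cleanly planning against delivery either, because 1.1.9 is a planning passage and already names three levels. Nor is coverage reported only at 8.6 throughout the plan: the physician's table is not tied to that value. The restriction belongs to the software comparison and the agreement analysis, and there threshold-free measures are used as well.

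A reader might infer four stronger things that the documents do not support.

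- *That coverage at 8.6 sits near its ceiling in patients planned to 15.3.* No section gives a coverage percentage at either level for any patient, and the target applies to an undefined share of the tumor.
- *That the targeted level goes unrecorded.* The case report form is not in the documents. Section 6.1.2 has a detailed description of the approved plan circulated and the actual light distribution calculated afterwards.
- *That dividing 45 J/cm² by each level gives treatment times.* That would hold only at a point kept at exactly the threshold irradiance. Fibers are placed sequentially, so irradiance at a point changes with each placement.
- *That pooling patients treated to different levels invalidates the primary test.* The exact binomial test in 12.1.3 still addresses the response rate under the planning strategy as applied.

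None of this answers the remaining points: the sections disagree, and agreement on coverage is tested at one of three permitted levels.

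**Conclusion.** The point holds in a limited form. Section 6.1.2 is inconsistent with itself, and its planning steps are inconsistent with 1.1.9 and 6.1.3, on whether there is one irradiance target or three. The permitted minimums span 1.78-fold, with no stated criterion for which applies. The DOSIE-COMSOL coverage comparison in 6.1.2 and 12.1.4 is made at one of the three levels, leaving two unchecked.

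This rests on the text and on one logical step: coverage at one threshold, with the minimum, average and maximum, does not determine coverage at another. It assumes nothing about how often the higher levels are used. If they never are, the inconsistency is only in the wording and the software comparison is unaffected. If they are used, the agreement analysis omits coverage at a level used for treatment. The documents do not allow an effect on the response rate or on the concordance coefficient to be calculated, and none is claimed. No view is taken on which level is right.

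**What to change.** 1. Reconcile 1.1.9, the planning and delivery steps of 6.1.2, section 6.1.3 and section 12.1.4 so that planning, delivery and analysis state the same target or targets. If more than one remains, say how the level for a given plan is determined. That choice is for the investigators.
2. In the software comparison of 6.1.2 and in 12.1.4, compute DOSIE-COMSOL agreement on percent coverage separately at 8.6, 10.8 and 15.3 mW/cm² for every Cohort A patient. Do not use each patient's own approval level. That would mix up to three thresholds in one concordance coefficient over 18 patients, and the coefficient depends on between-patient spread, which would then partly reflect the choice of threshold.
3. State whether the 5% rule applies to coverage at all three levels.
4. Record for each patient the level used to approve the plan and the percent of tumor volume reaching each of the three levels, and name these as variables for the irradiance-response objective.

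The cost is protocol wording, two extra agreement measures (three levels less the one already planned) and a few data fields. The irradiance maps come from simulations that the plan already requires, so no new patient procedure or sample size change is needed.

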6.1.4 Criteria for Retreatment

Retreatments with porfimer sodium are allowed per the approved indication. The retreatments will take place at the discretion of the treating physician, if an incomplete response is observed, and the participant had no SAEs from the first I-PDT and/or PDT treatment. Since the porfimer sodium is retained in the disease tissue for at least 3-4 weeks, there is no need for additional drug administration. Therefore, the retreatment will consist of an additional light administration only.

6.1.5 Dose Modification/ Reduction

There will be no dose modification or reduction of the porfimer sodium. The light dose may be reduced, at the discretion of the treating physician, in the retreatment sessions.

6.1.6 General Concomitant Medication and Supportive Care

Withholding of anticoagulation and antiplatelet agents prior to bronchoscopy/I-PDT and/or PDT will be determined per investigator discretion and the anesthesia preoperative team, as per Roswell Park standard of care (e.g., warfarin for 5 days, clopidogrel for 5 days, etc.).

Participants may be pre-treated for nausea and vomiting with appropriate anti-emetics.

There is a potential for an exacerbation of skin photosensitivity if porfimer sodium is used with other photosensitizing drugs. No drug interactions have been investigated.

The concomitant use of local anesthetics (infiltration anesthesia) is recommended and concomitant use of analgesics is also possible.

The use of antioxidants, including vitamin preparations, should be terminated on the day before treatment.

6.1.7 Precautions When Using Porfimer Sodium

Light-avoidance measures for approximately 30-90 days will be required. The clinical research coordinator and staff nurses will explain the light-avoidance measures to each subject, and a written instructions leaflet will be handed out to the subjects (**Appendix B**). The subject will be cautioned to protect the site of the infusion from excessive direct sunlight and certain bright lights for up to 3 months. The site may be exposed to normal ambient light.

Vital signs will be taken immediately after the end of the injection and 15 minutes after.

6.1.8 Duration of Treatment

The porfimer sodium photosensitizing drug will be given as a single dose 48 ± 4 hours (Day -2) before the EBUS I-PDT. The treatment is expected to be completed within a few hours.

6.1.9 Compliance

Any participant, who undergoes at least the EBUS-TBN guided I-PDT and/or I-PDT and/or PDT procedure and returns for the study follow-ups, is considered compliant when the treatment is administered.

6.1.10 Risks and Benefits

This is a Greater Than Minimal Risk study according to IRB criteria. Phototoxicity is the most likely potential risk associated with the systemic administration of the porfimer sodium. Proper shielding from the operating room lights will be maintained and the pulse oximetry sensor will be rotated every 20 - 30 minutes to minimize this risk. The subjects will be provided with written instructions on how to protect themselves from excessive light exposure.

The site-specific toxicity associated with this therapy includes:

- Injection site reaction: Very common effects include pain at the injection site (12%) which is transient and can be minimized by slowing the injection rate. Common effects include injection site reaction (3%) and burning sensation (3%).
- Tumor/local tissue reaction: Very common effects include pain (15%), hemorrhage (15%) and scarring (12%). Common effects include edema (8%), localized infection (8%), fever (8%), and skin necrosis (2%).
- Phototoxicity: Common effects include sunburn (3%), blisters (5%), erythema (5%), hyper-pigmentation (3%), and cutaneous photosensitivity (3%).
- Other systemic events: Constipation (11%), vomiting (9%), anemia (8%), nausea (6%), and giddiness (2%).

Potential Procedural Risks of EBUS-TBN Guided I-PDT and/or I-PDT and/or PDT

- Bronchial bleeding from the insertion site
- Extension of the bronchoscopic procedure duration
- Minimal risk of pneumothorax, infection, mediastinitis, allergic reaction to porfimer sodium
- Airway perforation

Standard of care palliative radiotherapy followed by I-PDT. It is not known what the risk is for administering the I-PDT two days after standard of care palliative radiotherapy.

Potential Benefits of the Proposed Research

For participants that have partial or complete response to I-PDT and/or PDT, the potential benefits include a significant reduction in tumor mass and symptoms. There is no guarantee of the outcome, nor is it possible to predict whether or not any specific participant will respond to porfimer sodium I-PDT and/or PDT.

The data that will be collected in this study will allow the research team to evaluate the safety and provide indication on the potential efficacy of this treatment. If shown to be safe, we will use this data to design Phase I/II studies to confirm safety and test the efficacy of EBUS-TBN guided I-PDT with porfimer sodium.

7 INVESTIGATIONAL PRODUCT

7.1.1 Active Substance and Source

The porfimer sodium for injection is supplied as a freeze-dried cake or powder as follows: NDC 76128-155-75, 75 mg vial.

7.1.2 Drug Shipment

Pinnacle Biologic, Inc. will ship porfimer sodium (Photofrin®) vials to Roswell Park to the Investigational Drug Service as per Roswell Park policy or to other enrolling study site. The receiving site will document the date of receipt and condition of the shipment. The investigational pharmacist or designee will retain drug shipment records.

The Photofrin® will be provided to the participants at no cost.

7.1.3 Preparation

Porfimer sodium will be prepared for injection following the manufacturer instructions: "Reconstitute each vial of porfimer sodium with 31.8 mL of either 5% Dextrose Injection (USP) or 0.9% Sodium Chloride Injection (USP), resulting in a final concentration of 2.5 mg/mL. Shake well until dissolved. Do not mix porfimer sodium with other drugs in the same solution. Porfimer sodium, reconstituted with 5% Dextrose Injection (USP) or with 0.9% Sodium Chloride Injection (USP), has a pH in the range of 7 to 8. Porfimer sodium has been formulated with an overage to deliver the 75 mg labeled quantity. The reconstituted product should be protected from bright light and used immediately. Reconstituted porfimer sodium is an opaque solution, in which detection of particulate matter by visual inspection is extremely difficult. Reconstituted porfimer sodium, however, like all parenteral drug products, should be inspected visually for particulate matter and discoloration prior to administration whenever solution and container permit area from light."

